8.3.6. Pregnancy

- Details of all pregnancies that occur in female participants after the start of study intervention, from the time the ICF was signed until 30 days after the last dose of study intervention, will be collected.
- If a pregnancy is reported, the investigator should inform the sponsor within 24 hours of learning of the pregnancy and should follow the procedures outlined in [Appendix 7](#).

- Abnormal pregnancy outcomes (eg, spontaneous abortion, fetal death, stillbirth, congenital anomalies, ectopic pregnancy) or genetic abnormalities (whether leading to an elective abortion or not) are considered SAEs.

8.3.7. Potential Hy's Law Cases

Criteria for possible Hy's law cases are as follows:

- ALT or AST $\geq 3 \times$ ULN AND
- Total bilirubin $\geq 2 \times$ ULN AND
- ALP $< 2 \times$ ULN

Study site personnel must report every participant who meets the criteria for potential Hy's law as SAEs (see [Appendix 9](#) for a detailed description on handling potential Hy's law cases and liver toxicity). Typically, all analytes will be obtained from the same sample, but they may come from multiple samples taken within a 24-hour period. This requirement applies from the time the participant signs the ICF for the study until 30 days after the last known dose of study intervention.

Additional details regarding liver safety assessments and follow-up are provided in [Appendix 9](#).

8.3.8. Medication Errors

Medication error refers to any unintended error in the dosing and/or administration of the study intervention as per instructions in the protocol. Medication errors generally fall into 4 categories as follows:

- Wrong study drug/device
- Wrong dose (including dosing regimen, strength, form, concentration, amount)
- Wrong route of administration
- Wrong participant (ie, not administered to the intended participant)

Medication errors include occurrences of overdose and underdose of the study intervention.

Overdose: Unintentional administration of a quantity of the study intervention given per administration or per day that is above the maximum recommended dose according to the reference safety information or protocol for the study intervention or comparator as applicable. This also takes into account cumulative effects due to overdose.

Underdose: Unintentional administration of a quantity of the study intervention given per administration or per day that is under the minimum recommended dose according to the reference safety information or protocol.

8.4. Treatment of Overdose

The sponsor does not recommend specific treatment for an overdose.

In the event of an overdose, the investigator should:

1. Contact the medical safety physician (MSP) immediately.
2. Closely monitor the participant for any AE/SAE and laboratory abnormalities until study treatment can no longer be detected systemically.
3. Document the quantity of the excess dose as well as the duration of the overdose in the site's source documents for the participant.

Decisions regarding dose interruptions or modifications will be made by the investigator in consultation with the MSP based on the clinical evaluation of the participant.

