Linaclotide is a 14-amino acid peptide that acts on the apical surface of epithelial cells surrounding the intestinal lumen to stimulate the guanylate cyclase subtype C (GC-C) receptor. Linaclotide is approved for the treatment of irritable bowel syndrome with constipation (IBS-C) and chronic idiopathic constipation (CIC) in the United States, Canada, Japan, Australia, New Zealand, Kingdom of Saudi Arabia, and Mexico; for the treatment of IBS-C in China, the European Union (EU), Hong Kong, Macau, and Switzerland; and is being studied in other regions. By activating GC-C, orally administered linaclotide has been found to increase intestinal fluid secretion and intestinal transit, and to decrease visceral (abdominal) pain. Linaclotide has minimal oral bioavailability ($\leq 0.2\%$) in several animal species (Bryant 2010; Eutamene 2010) and is minimally absorbed with low systemic availability in adults. Refer to the Investigator's Brochure (IB) for a more detailed description of the chemistry, pharmacology, efficacy, and safety of linaclotide, based on studies conducted in animals, healthy volunteers, and in participants with IBS-C and CIC (linaclotide IB).

Two Phase 2 dose-ranging studies have been conducted with linaclotide in pediatric participants; one in FC, 6 to 17 years of age (LIN-MD-62), and one in IBS-C, 7 to 17 years of age (LIN-MD-63). Results from these two studies are summarized in Section 2.2.2.

This study will assess the long-term safety of linaclotide administered to pediatric participants with FC (total exposure with linaclotide for 24 weeks) or IBS-C (total exposure with linaclotide for 52 weeks) who have completed Study LIN-MD-62, LIN-MD-63, or LIN-MD-64:

- LIN-MD-62 (Phase 2): A Multicenter, Randomized, Double-blind, Placebo-controlled, Parallel-group, Safety and Efficacy Study of a Range of Linaclotide Doses Administered Orally to Children, Ages 6 to 17 Years, Who Fulfill Modified Rome III Criteria for Child/Adolescent FC
- LIN-MD-63 (Phase 2): A Multicenter, Randomized, Double-blind, Placebo-controlled, Parallel-group, Safety and Efficacy Study of a Linaclotide Dose Administered Orally to Children, Ages 7 to 17 Years, With Irritable Bowel Syndrome With Constipation (IBS-C) (ie, Fulfill Rome III Criteria for Child/Adolescent IBS and Fulfill Modified Rome III Criteria for Child/Adolescent Functional Constipation)

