A total of 173 participants were randomized to receive 1 of 3 proposed linaclotide doses (Dose A, B, or C in 116 participants), the approved adult linaclotide dose (145 μ g in 16 participants), or placebo (41 participants) for 4 weeks of study intervention followed by a 1-week Postintervention Period. For the primary and key secondary endpoints of the study, none of the 3 linaclotide doses (A [low dose], B [medium dose], and C [high dose]) indicated clear improvement over placebo (p -value \geq 0.1502) based on analysis of the ITT Population. However, a numerical trend toward efficacy at the higher doses was observed for the primary endpoint of change from baseline in 4-week overall SBM frequency rate (SBMs/week). Overall, linaclotide was well tolerated across all doses and both age groups. The safety profile was consistent with prior adult linaclotide studies for CIC. The most frequently reported TEAE was diarrhea, which occurred in 7.6% of linaclotide-treated participants versus 0% in the placebo group. The majority of the TEAEs of diarrhea reported were mild; none were severe. In the 12 to 17 years of age group, one participant experienced moderate diarrhea (related) leading to discontinuation in the linaclotide Dose C group.

There were no reported AESIs (ie, significant volume depletion and/or significant electrolyte abnormalities and/or ECG abnormalities that are considered by the investigator or sponsor to be related to diarrhea) or deaths. There were 2 SAEs, neither of which were diarrhea, in participants in the 12-17 years of age group, neither were considered related to study intervention. In the younger pediatric participants, 6 to 11 years of age, no SAEs or AEs leading to discontinuation were reported.

As with adults, linaclotide is minimally absorbed with low systemic availability in this pediatric population.

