2.2.3. Other Nonclinical Information

2.2.3.1. Non-clinical Toxicology

In nonclinical studies, oral administration of linaclotide at 10 µg/kg/day caused deaths in young neonatal mice (human age equivalent of approximately 0 to 28 days old). These deaths were due to rapid and severe dehydration produced by significant fluid shifts into the intestinal lumen resulting from GC-C agonism in neonatal mice. Supplemental subcutaneous fluid administration prevented death after linaclotide administration in neonatal mice. Tolerability to linaclotide increases with age in juvenile mice. In 2-week-old mice, linaclotide was well tolerated at a dose of 50 µg/kg/day, but deaths occurred after a single oral dose of 100 µg/kg. In 3-week-old mice, linaclotide was well tolerated at 100 µg/kg/day, but deaths occurred after a single oral dose of 600 µg/kg. Significantly higher doses (≥ 200 times the clinically relevant adult dose) were tolerated in 4-week-old juvenile mice, human age equivalent of approximately > 2 to 7 years of age without supplemental fluid administration. Based on these nonclinical results, the Linzess PI has a contraindication in pediatric patients less than 6 years of age and a boxed warning regarding its use in pediatric patients.

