2.2.4. Post-marketing Experience

In post-marketing experience, severe diarrhea AEs associated with dizziness, syncope, hypotension, and electrolyte abnormalities (hypokalemia and hyponatremia) requiring hospitalization or IV fluid administration have been reported in adult patients treated with linaclootide.

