8.5. Pharmacokinetics

Not applicable

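### The overdose rule in Protocol 8.4 ends close monitoring on systemic drug detectability, which the study does not measure and which does not track the risk in the gut

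*Protocol*

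**What the plan says.** Protocol Section 8.4 recommends no specific treatment for an overdose and gives three instructions: contact the medical safety physician immediately, monitor, and document the excess dose. The monitoring instruction, item 2, reads: "Closely monitor the participant for any AE/SAE and laboratory abnormalities until study treatment can no longer be detected systemically". It is the only end point in either document for close monitoring after an overdose. The section closes by basing decisions on interrupting or changing the dose on the clinical evaluation of the participant, in consultation with the same physician. It does not extend that basis to the length of monitoring.

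Section 8.5, Pharmacokinetics, reads "Not applicable". The Introduction (Section 2) says the drug "acts on the apical surface of epithelial cells surrounding the intestinal lumen", and Section 2.2.2 adds that "linaclotide is minimally absorbed with low systemic availability in this pediatric population". The SAP does not mention overdose.

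**The concern.** A stop rule for safety monitoring should be something a site can determine, and it should indicate that the hazard is over. This one appears to fail on both counts. Nobody in the study measures linaclotide in blood, and the hazards the protocol describes arise in the intestinal lumen, not in the circulation.

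At stake is how long a child who has taken too much, and who looks well, is watched closely. The participants are children, and doses after the Day 1 visit are taken at home. If the stop point says nothing about hydration or electrolytes, the decision to stop watching rests on the wrong fact.

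**Working it through.** No arithmetic settles this; the check sets the sections side by side.

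**1. Can a site apply the criterion?** Sections 8.5 (Pharmacokinetics) and 8.6 (Pharmacodynamics) both say not applicable. Table 10-1 lists hematology, chemistry, urinalysis, a urine alcohol and drug screen, and pregnancy tests. In the two documents:
- linaclotide assays planned: 0
- clearance times or half-lives given: 0
- observation periods after an overdose: 0

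Section 2 refers to the Investigator's Brochure for pharmacology. That document was not available and might give a clearance time, but Section 8.4 does not cite it.

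**2. Would the criterion be informative if it could be applied?**
- Site of action: the luminal surface of the intestine (Section 2).
- Absorption: "Linaclotide has minimal oral bioavailability", put at no more than 0.2% in several animal species (Section 2). It is described as minimal in adults (Section 2) and in both pediatric Phase 2 studies (Section 2.2.2).
- Nonclinical hazard (Section 2.2.3.1), in neonatal mice: "These deaths were due to rapid and severe dehydration produced by significant fluid shifts into the intestinal lumen".
- Clinical hazard (Section 2.2.4), in treated adults: "severe diarrhea AEs associated with dizziness, syncope, hypotension, and electrolyte abnormalities (hypokalemia and hyponatremia) requiring hospitalization or IV fluid administration".
- Events of special interest (Section 8.3.1): volume depletion, electrolyte or ECG abnormalities attributed to diarrhea.

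Each hazard follows from the effect in the gut. On the protocol's own account, a drug can be absent from blood while fluid loss continues. A clearance time from the Investigator's Brochure would make the criterion usable but would not remove this mismatch.

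**3. Whom does it affect?**
- *A participant with an adverse event after overdose.* Signs, symptoms and sequelae of an overdose are adverse events (Section 10.3.1) and are followed to resolution or stabilization (Sections 8.2 and 8.3.4). Item 2 does not shorten this.
- *A participant with a clinically significant laboratory value.* The test is repeated until the value is normal, back to baseline or no longer significant (Section 8.2.4).
- *Intentional overdose.* Section 7.1.1 lists it, subject to investigator discretion, among the reasons for mandatory discontinuation. Discontinued participants must return for end-of-treatment assessments, which include chemistry, ECG, physical examination and postural vital signs (Sections 10.10.7 and 10.10.11). Where self-harm intent is possible, Section 10.3.1 requires reporting whatever the sequelae.
- *Unintentional overdose, nothing found yet.* Section 10.3.1 does not make the overdose itself an adverse event, so follow-up to resolution is not triggered. Item 2 sets the end of close monitoring. This is the affected group.

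**4. Does the ordinary schedule supply a close watch for that group?** After the Day 1 visit, postural vital signs are taken at every on-site visit. From the schedules of activities, the longest planned interval between on-site visits is 169 − 113 = 56 days in FC and 365 − 281 = 84 days in IBS-C. Chemistry is scheduled once after the first dose, at end of treatment. These are useful background checks, but not a post-overdose watch.

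**The case against.** The strongest reply is that the clause does little harm because other rules surround it. Section 8.2 has severe diarrhea, particularly with dehydration or electrolyte or ECG changes, actively monitored throughout the study, with no drug-level stop point. Section 8.3.2 collects adverse events until 30 days after the last dose. Sections 8.3 and 10.3.1 call for particular attention to diarrhea. Section 8.4 brings in the medical safety physician at once, who can set a sensible period. All of this stands. A reader might infer that item 2 is the only rule on how long to keep looking at a well participant; the documents do not support that. It is the only end point for the intensified monitoring.

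A second reply is that the direction of any error is unknown. A reader might infer that monitoring would stop at once because little drug reaches the blood. Equally, a site with no assay cannot show that the criterion has been met, which could prolong monitoring or prompt a call to the sponsor. The text does not decide between these. Nor does the animal bioavailability figure: detectability depends on assay sensitivity, not on the fraction absorbed.

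A third reply is that danger from an overdose in this age range is not shown. This also stands. Doses at least 200 times the clinically relevant adult dose "were tolerated in 4-week-old juvenile mice, human age equivalent of approximately" more than 2 to 7 years, and the post-marketing reports concern treated adults, not overdose. The link from hazard to overdose is inferred.

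None of these replies makes the criterion fit the risk it is meant to bound.

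**Conclusion.** The point holds, and it is minor. The end point for close monitoring after an overdose depends on a quantity that the study does not measure and that does not indicate whether the fluid and electrolyte risk has passed. This is a wrong rule, not merely a missing detail.

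Its reach is narrow: the end of intensified monitoring after an unintentional overdose, in a participant with no adverse event or laboratory abnormality yet, after the medical safety physician has been contacted. The documents give no overdose frequency, so no count of affected participants can be offered. No endpoint, population or planned analysis changes.

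Confidence is high on the text and lower on the consequence. The conclusion assumes that the hazards described for ordinary treatment in adults and for young mice are also the ones to watch for after an overdose in a child. It does not assume that harm is likely.

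**What to change.** In Section 8.4 item 2, replace the detectability clause with a clinical stop point, for example: *for an observation period agreed with the medical safety physician at the initial contact, and thereafter until any diarrhea has resolved and hydration status, postural vital signs and any electrolytes obtained are normal or at baseline.*

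The documents support no particular number of hours, so the period is left to clinical judgment at the contact Section 8.4 already requires. The sponsor's medical safety function may print a fixed default if it prefers one.

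The cost is one clause in the next amendment. In conduct, a well participant needs one or two phone contacts. Occasionally there would be an unscheduled visit, which needs sponsor approval under the schedule footnotes, or a blood draw where clinically indicated. Section 8 already allows unscheduled safety samples. The visit schedule and the SAP stay as they are.

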8.5. Pharmacokinetics

Not applicable

8.6. Pharmacodynamics

Not applicable

8.7. Genetics

Not applicable

8.8. Biomarkers and Other Assessments

Not applicable

8.9. Health Economics

Not applicable

9. Statistical Considerations

9.1. Statistical Hypotheses

There are no preconceived statistical hypotheses to be assessed in this long-term safety study.

9.2. Sample Size Determination

At least 120 participants are planned to be enrolled in this long-term safety study, LIN-MD-66. However, the actual number of participants in this study will depend on the number of participants who complete the lead-in studies (LIN-MD-62, LIN-MD-63, and LIN-MD-64) and who are eligible to be enrolled into this long-term study after fulfilling the eligibility criteria. The sample size in this study is not driven by any statistical consideration.

9.3. Populations for Analyses

For this long-term safety study, only 1 analysis population, ie, Safety Population, is considered. The Safety Population is defined as all treated study participants who receive/take ≥ 1 administration of study intervention in this study. Participants will be summarized according to the study intervention they actually received.

9.4. Statistical Analyses

The Statistical Analysis Plan (SAP) will be developed and finalized before database lock.

The summary of the other efficacy endpoint of proportion of participants who no longer fulfill Rome III criteria at the end of the study intervention period will be discussed in the SAP.

This section is a summary of the planned statistical analyses for safety. Further details will be included in the SAP. All safety analyses or summaries will be performed using the Safety Population, for overall and for each age group (unless mentioned otherwise) by study intervention group separately for the FC and IBS-C pediatric populations.

The safety parameters will include AEs, clinical laboratory parameters, vital sign measurements, weight, height, and ECG parameters. For each safety parameter, the baseline value for all analyses of the corresponding safety parameter (laboratory, vital signs, body weight, height, and ECG) will be defined as below:

- 1) If participants enroll into LIN-MD-66 within 28 days of last dose date of the lead-in study, baseline of the lead-in study will be used as the baseline value in LIN-MD-66.
- 2) If participants enroll into LIN-MD-66 after 28 days of last dose date of the lead-in study, the last non-missing assessment made before the first dose of study intervention in this study will be used as the baseline value in LIN-MD-66.

Safety data analyses will be provided descriptively based on the observed safety data, without data imputation for missing safety parameter assessment(s).

9.4.1. Adverse Events

AEs will be coded using the Medical Dictionary for Regulatory Activities (MedDRA), Version 23.0 or newer.

An AE will be considered a TEAE if:

- The AE began on or after the date of the first dose of study intervention in LIN-MD-66; or
- The AE was present before the date of the first dose of study intervention in LIN-MD-66 but increased in severity or became serious on or after the date of the first dose of study intervention in LIN-MD-66.

An AE that occurs more than 1 day after the last dose of study intervention in LIN-MD-66 will not be counted as a TEAE.

An AE will be considered a treatment-emergent SAE (TESAE) if it is a TEAE that additionally meets any SAE criteria.

The number and percentage of participants reporting TEAEs in each study intervention group will be tabulated by SOC and preferred term and by SOC, preferred term, and severity.

The number and percentage of participants reporting treatment-related TEAEs in each study intervention group will be tabulated by SOC and preferred term.

If more than 1 AE is coded to the same preferred term for the same participant, the participant will be counted only once for that preferred term using the most severe and most related occurrence for the summarizations by severity and by relationship to study intervention.

Summary tables will be provided for participants with TESAEs, AESIs, and participants with TEAEs leading to discontinuation if 5 or more participants reported such events. Listings of all AEs, SAEs, AESIs, and AEs leading to discontinuation by participant will be presented.

The definitions of an AE and SAE can be found in [Appendix 3](#).

9.4.2. Clinical Laboratory Assessments

Descriptive statistics for clinical laboratory values (in SI units) at baseline and changes from baseline at each assessment timepoint will be presented by study intervention group for each clinical laboratory assessment.

The criteria for PCS laboratory values will be detailed in the SAP. The number and percentage of participants who have PCS postbaseline clinical laboratory values will be tabulated by study intervention. The percentages will be calculated relative to the number of participants who have available non-PCS baseline values and at least 1 postbaseline assessment. The numerator will be the total number of participants with at least 1 PCS postbaseline value. A supportive listing of participants with PCS postbaseline values will be provided for the Safety Population.

9.4.3. Vital Signs

Descriptive statistics for height, weight, and vital signs (supine systolic and diastolic blood pressure, supine pulse rate, respiration rate, and temperature) at baseline and changes from baseline at each assessment timepoint will be presented by study intervention.

Vital sign values will be considered to be PCS values if they meet both the observed-value criteria and the change-from-baseline-value criteria (as defined in the SAP). The number and percentage of participants who have PCS postbaseline vital sign values will be tabulated by study intervention group. The percentages will be calculated relative to the number of participants who have available non-PCS baseline values and at least 1 postbaseline assessment. The numerator will be the total number of participants with at least 1 PCS postbaseline value. A supportive listing of participants with PCS postbaseline values will be provided for the Safety Population.

